**【Setting basis】**

1. 3-8.16. 18-20 are set to ensure the safety of the subjects.
2. 9.10(1)-(5).11-15 are set a certain standard for the target subjects after considering the influence on the safety assurance of the subjects and the evaluation of efficacy.
- 8.9. is set to eliminate the effects of other drugs in the accurate evaluation of efficacy.
- 10(6). is set to eliminate drugs that cause interaction by the medical efficacy of this investigational drug.
17. is set to ensure the safety of patients with complications that are expected to have an effect due to the medical efficacy and adverse drug reaction of this investigational drug.
21. In addition to the above items, this is set assuming that the principal investigator or sub-investigator is judged to be inappropriate for this clinical trial in light of scientific and ethical aspects.

clinical trial protocol 番号 : YCU-21001

## 5 Subject consent acquisition and information provision

### 5.1 Explanatory document / consent document

The principal investigator prepares explanatory and consent documents and amends them if necessary. The principal investigator obtains approval in advance from the institutional review board for the documents that are created and amended.

The following are kept in mind when creating an explanatory document:

1. Do not use words that cause the subject to waive their rights or consider doing so, or threaten/eliminate the legal liability of the principal investigator, sub-investigator, clinical trial collaborators, and involved medical institution.
2. Use non-technical terms as much as possible so that the subject can understand them.

### 5.2 Description

The principal investigator creates an explanatory document that includes at least the following contents:

1. That the clinical trial involves research
2. Purpose of the clinical trial
3. Principal investigator or sub-investigator name, job title, and contact information
4. Clinical trial method
5. Expected clinical benefits and risks or inconveniences
6. Presence or absence of other treatments and tests for the subject, and the expected significant benefits and risks associated with those treatments and tests.
7. Subject's planned participation period in the clinical trial
8. Statement that participation in the clinical trial is voluntary and that the subject may refuse treatment or withdraw from the clinical trial at any time. The refusal or withdrawal does not result in any adverse treatment of the subject or loss of benefits that would be incurred if the subject did not participate in the trial.
9. Monitors, auditors, institutional review boards, regulatory agencies, and other relevant individuals/groups should be able to view medical source documents with the subject's confidentiality preserved. The subject must provide a signed consent document to allow viewing.
10. Subject confidentiality should be preserved even when clinical trial results are published.
11. The contact person at the involved medical institution should respond if the subject wishes to obtain further information regarding the clinical trial and the subject's rights, or if there is a health hazard related to the clinical trial.
12. Compensation and treatment available to subjects in the event of clinical trial-related health hazards
13. Number of subjects planning to participate in the clinical trial
14. Statement that subjects will be promptly informed when information becomes available that may affect the subject's willingness regarding continued participation in the clinical trial
15. Conditions or reasons for terminating participation in clinical trials
16. If the subject needs to bear the cost, the details
17. If money is paid to the subject, the details
18. Responsibilities of the subject

### 5.3 Consent acquisition period and method

The principal investigator or sub-investigator should give the explanatory document and consent document approved by the institutional review board to the subject before the subject participated in this clinical trial, and fully explain the details. After answering questions from the subject and confirming that the subject fully understands the clinical trial, the subject voluntarily consents to

clinical trial protocol 番号 : YCU-21001

participate in the clinical trial by signing the document. The document also explains that the information obtained from participating in this clinical trial may be used for future studies. If this point is refused, the information will not be used for other research.

The principal investigator or sub-investigator who explained the details is also identified on the document and provides their seal on or signs the consent document. The date when the explanation was given to the subject is included in the document. If the clinical trial collaborators give a supplementary explanation, the clinical trial collaborators should also be registered, stamped, or signed, and the date should be entered.

#### 5.4 Amendment of explanatory document/consent document

If any information is available that may affect the subject's will while the subject is participating in this trial, the principal investigator or sub-investigator must promptly convey the information to the subject, record the subject's intention to continue participation. If the principal investigator deems it necessary, the explanatory and consent documents are amended and approval is obtained from the institutional review board. In this case, the change will be explained using the board-approved amended document and consent document, and the subject's signed re-consent will be obtained.

### 6 Subject registration

Participation in this clinical trial is by a registration system operated by the Case Registration Center. The registration procedure is detailed below.

#### 6.1 Registration procedure

The principal investigator or sub-investigator obtains written consent from the candidate subject. The principal investigator or sub-investigator will enter the subject in the screening list and assign the subject identification code to the subjects who have provided their consent, and confirm their eligibility according to "エラー! 参照元が見つかりません。 エラー! 参照元が見つかりません。" and "エラー! 参照元が見つかりません。 エラー! 参照元が見つかりません。". If it is determined that there is no problem with eligibility, the principal investigator or sub-investigator, and clinical trial collaborators enter the necessary information into the electronic data capture (EDC) system and register at the time of V2. If there is no problem with eligibility, a case registration number will be issued. Registration is completed with this number. The details of the registration procedure are shown in the procedure manual specified separately.

#### 6.2 Randomization method

At the time of enrollment, subjects will be assigned to one of the two groups described in "エラー! 参照元が見つかりません。 エラー! 参照元が見つかりません。" at a ratio of 1:1 using the allocation table prepared by the substitution block method. No adjustment factor is set. The applicable allocation number will be issued via the EDC system.

clinical trial protocol 番号 : YCU-21001

## 7 Investigational drug

## 7.1 Investigational drug code: WY-8678

## 7.2 Active ingredient and content of investigational drug, dosage form, etc.

- Each tablet contains guanabenz acetate 2.525 mg (2 mg as guanabenz)
- White circular, scored, uncoated lock

## 7.3 Details of investigational drug

1.

Name: WYTENS® tablet, 2 mg

[figure not shown]
Generic name: guanabenz acetate

Chemical name: (E)-1-(2,6-Dichlorobenzylideneamino) guanidine monoacetate

Molecular formula:  $C_8H_8Cl_2N_4 \cdot C_2H_4O_2$ 

Molecular weight: 291.13

Structural formula:

## 7.4 Packaging form and labeling

## 7.4.1 Packaging form

1. WY-8678

- Enclosed in one box (for each case) where WY-8678 is enclosed in a 5-pack in the following form:

4 mg/day

1 week: 14 tablets (1 tablet, 2 mg) per press-through package (PTP) sheet

4 weeks: 4 sheets per pack (aluminum packaging bag)

16 weeks + reserve drug (4 weeks): 5 packs per box per case

8 mg/day

1 week: 14 tablets (1 tablet, 2 mg), 2 PTP sheets

4 weeks: 8 sheets per pack (aluminum packaging bag)

16 weeks + reserve drug (4 weeks): 5 packs per box per case

## 7.4.2 Labeling

For 4 mg/day

clinical trial protocol 番号 : YCU-21001

For clinical trial 4mg/day Allocation number:
 
WY-8678
 
Content: 14 tablets × 4 sheets × 5 bags  Storage method: Room temperature  Serial number: GK27  Expiration date: 2025.9
 
Yokohama City University Hospital, Department of Palliative  Medicine Clinical Instructor: [name]
 
[name]

---

For 8 mg/day

For clinical trial 8 mg/day Allocation number:
 
WY-8678
 
Content: 14 tablets × 8 sheets  Storage method: Room temperature  Serial number: GK27  Expiration date: 2025.9
 
Yokohama City University Hospital, Department of Palliative  Medicine Clinical Instructor: [name]
 
[name]

---

Fig. 7.4.2-1 Labeling of WY-8678

## 7.5 Management of investigational drug

Shown separately in “Manual for investigational drug management”

## 8 Clinical trial design and clinical trial schedule

### 8.1 Clinical trial design

#### 8.1.1 Clinical trial method

Single-center, randomized

#### 8.1.2 Group composition

Subjects confirmed to be eligible during the screening period will be assigned to the following two groups at a ratio of 1 : 1 : 1 at the time of enrollment.

Group A: WY-8678 4 mg/day

Group B: WY-8678 8 mg/day

#### 【Setting basis】

To determine drug efficacy two approved dose groups are set (4 mg/day and 8 mg/day). The efficacy of each group is evaluated instead of a parallel-group comparison.

#### 8.1.3 Usage/dose of investigational drug, route of administration, administration period

During the treatment period, the investigational drug is orally administered to groups A and B twice daily for 16 weeks. The number of administered tablets in each group is as follows:

clinical trial protocol 番号 : YCU-21001

- Group: WY-8678, 4 mg/day: one tablet per session, twice a day
- B group: WY-8678, 8 mg/day: 2 tablets per session, twice a day

The investigational drug is first taken after dinner the day of visit 2 (V2). The final administration timing should be the morning of V7 at 16 weeks.

#### 【Setting basis】

- Dosage / administration method:

To explore the efficacy of guanabenz acetate, the approved doses of 4 mg and 8 mg were used. In a phase II pilot study, the antihypertensive effect of guanabenz acetate was slow and there was no significant difference in the incidence of adverse drug reactions between the 4 mg and 8 mg starting doses. All of them are in the approved dose range. The doses were set because the clinical data showed that the start of administration from 8 mg also ensured sufficient safety. After confirming the POC in this study, we plan to investigate the appropriate dose of the drug in a Phase IIb study.

- Administration period:

Globally, short-term clinical trials for NAFLD (e.g., NCT02913105 Safety, Tolerability, Pharmacokinetics and Efficacy of LMB763 in Patients With NASH; NCT02927314 A Study of the Efficacy and Safety of CF102 in the Treatment of Non-Alcoholic Fatty Liver Disease) have a minimum dosing period of 12 weeks. No significant difference was found in PDFF in a 12-week study with PDFF as the primary endpoint. However, in this study, the rate of change in hepatic fat mass from image evaluation by MRI-PDFF is the primary endpoint. Therefore, it was considered that a certain administration period was required to confirm the efficacy of this drug, and 16 weeks was judged to be the appropriate period.

#### 8.1.4 Scheduled participation period of subjects

The study consists of an 8-week screening period, a 16-week treatment period, and a 4-week follow-up (the final timing of administration of the investigational drug is the morning of V7 at 16 weeks). The investigational drug is orally administered twice daily for 16 weeks.

#### 8.2 Clinical trial period (planned)

May 1, 2021 to June 30, 2023

(Consent acquisition period: September 1, 2021 to July 31, 2022)

#### 8.3 Concomitant treatment

##### 8.3.1 Drugs/treatments prohibited for concomitant use

1. The following drugs are prohibited from concomitant use from the time of consent acquisition to the treatment period:
  - (1) Ursodeoxycholic acid
  - (2) Guanabenz analogs (clonidine, methyldopa)
  - (3) Thiazolidine, glucagon-like peptide-1 (GLP-1) receptor agonist, SGLT2 inhibitor, insulin
  - (4) Central nervous system depressants (barbital, sodium thiopental, morphine hydrochloride hydrate, brotizolam, diazepam)
  - (5) Vitamin E

clinical trial protocol 番号 : YCU-21001

- (6) NAFLD-related drugs (amiodarone, methotrexate, systemic glucocorticoids, tetracycline, tamoxifen, higher doses of estrogen, anabolic steroids, or valproic acid than used for hormone replacement) or other hepatotoxins
- (7) Drugs that significantly affect body weight (including over-the-counter weight loss drugs)

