	
③ Inflammation in the lobules (0-3 points)
 
 
5. Patients with magnetic resonance imaging (MRI)-proton density fat fraction (PDFF) liver fat mass <math>\geq 8\%</math> at screening.
 
6. Patients with magnetic resonance elastography (MRE) value <math>\leq 3.6</math> kPa at screening.
 
7. Patients with a body mass index (BMI) <math>\geq 25</math> kg/m^2 at the time of screening.
 
8. Patients receiving diet or exercise therapy 12 weeks before screening, with no improvement.
 
9. Patients who are willing to maintain a stable diet and physical activity during the clinical trial.
 
 
Exclusion criteria
 
 
1. Pregnant, lactating, potentially pregnant women, or patients who do not agree to contraception during the trial period.
 
2. Patients who have taken guanabenz acetate within 16 weeks prior to screening or who have participated in other clinical studies (observational studies are excluded).
 
3. Patients with drug allergies to guanabenz acetate.
 
4. Patients with liver failure or cirrhosis.
 
5. Patients with the following laboratory test values: 
 
(1) Alanine aminotransferase (ALT) <math>> 430</math> IU/L (males) or <math>> 240</math> IU/L (female); or aspartate aminotransferase (AST) <math>> 300</math> IU/L (males and females)
 
(2) Prothrombin time-international normalized ratio (PT-INR) <math>\geq 1.5</math> (excluding anticoagulant therapy)
 
(3) Total bilirubin value <math>> 2.0</math> mg/dL (excluding definitive diagnosis of Gilbert syndrome)
 
(4) Platelet count <math>< 80,000/\mu\text{L}</math>
 
(5) Estimated glomerular filtration ratio (eGFR) <math>< 45</math> (calculated by body surface area correction: standardized eGFR)
 
 
 
6. Patients with a history of acute or chronic liver disease other than NAFLD/NASH and complications: 
 
(1) Patients suffering from hepatitis B (defined by hepatitis B surface (HBs) antigen positive at the time of screening) or hepatitis C (defined by hepatitis C virus (HCV) antibody positive at the time of screening). However, anti-HCV antibody positive patients who are judged to be negative for hepatitis C virus ribonucleic acid (HCV-RNA) can be registered if they can be confirmed to be negative for at least one year before screening.
 
(2) Patients with autoimmune hepatitis.
 
(3) Patients with primary biliary cholangitis, primary sclerosing cholangitis, Wilson's disease, <math>\alpha</math>1-antitrypsin deficiency, hemochromatosis or iron overload, drug-induced or alcoholic liver disease, or a history of known biliary atresia.
 
 
 

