#### 4.3 Exclusion criteria

Patients who meet the following criteria at the time of screening are excluded:

1. Pregnant, lactating, potentially pregnant women, or patients who do not agree to contraception during the trial period.
2. Patients who have taken guanabenz acetate within 16 weeks prior to screening or who have participated in other clinical studies. Observational studies are excluded.
3. Patients with drug allergies to guanabenz acetate.
4. Patients with liver failure or cirrhosis.
5. Patients with the following laboratory test values:
  - (1) ALT  $> 430$  IU/L (males) or  $> 240$  IU/L (females); or AST  $> 300$  IU/L
  - (2) PT-INR  $\geq 1.5$  (excluding anticoagulant therapy)
  - (3) Total bilirubin value  $> 2.0$  mg/dL (excluding definitive diagnosis of Gilbert syndrome)
  - (4) Platelet count  $< 80,000/\mu\text{L}$
  - (5) eGFR  $< 45$  (calculated by body surface area correction: standardized eGFR)
6. Patients with a history of acute or chronic liver disease other than NAFLD/NASH and complications:
  - (1) Patients suffering from hepatitis B (HBs antigen positive at the time of screening) or hepatitis C (HCV antibody positive at the time of screening).  
HCV antibody-positive patients who are negative for HCV-RNA can be registered if they are confirmed to be negative for at least one year before screening.
  - (2) Patients with autoimmune hepatitis.
  - (3) Patients with primary biliary cholangitis, primary sclerosing cholangitis, Wilson's disease,  $\alpha$ 1-antitrypsin deficiency, hemochromatosis or iron overload, drug-induced or alcoholic liver disease, or a history of known biliary atresia.
  - (4) Patients with suspicion or definitive diagnosis of hepatocellular carcinoma.
7. Patients with a history of HIV infection.
8. Patients with findings of portal hypertension (complications include ascites, hepatic encephalopathy, varicose veins, and splenomegaly).
9. Patients with a history of use of NAFLD-related drugs (amiodarone, methotrexate, systemic glucocorticoids, tetracycline, and tamoxifen, or higher doses of estrogen, anabolic steroids, or valproic acid than used for hormone replacement) or other hepatotoxins for at least 4 weeks prior to screening.
10. Patients who have used the following drugs:

clinical trial protocol 番号 : YCU-21001

- (1) Insulin, glucagon-like peptide-1 (GLP-1) receptor agonists, sodium-glucose transport protein 2 (SGLT2) inhibitors, or thiazolidine 12 weeks before screening

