  - (2) Ursodeoxycholic acid or vitamin E 12 weeks before screening
  - (3) Altered doses of dyslipidemia drugs or antihypertensive drugs 12 weeks before screening
  - (4) Altered dose of oral diabetes treatment drug (DPP-4 inhibitor, SU preparation,  $\alpha$ -glucosidase inhibitor, metformin) 12 weeks before screening
  - (5) Those with a significant effect on body weight (including over-the-counter drugs for weight loss) 12 weeks before screening
  - (6) Central nervous system depressants (barbital, sodium thiopental, morphine hydrochloride hydrate, brotizolam, diazepam, etc.)
11. Patients with 10% weight change 24 weeks before screening.
  12. Patients scheduled to undergo surgery after obesity surgery (such as gastroplasty and Roux-en-Y gastric bypass surgery) or during the trial period.
  13. Patients with a history of type 1 diabetes.
  14. Patients with HbA1c > 9.5% at screening or with uncontrolled type 2 diabetes.
  15. Patients with hyperthyroidism or hypothyroidism, or with screening results showing thyroid dysfunction. For hypothyroidism, registration is possible if thyroid replacement therapy is received 12 weeks before screening and the test values are stable.
  16. Patients with a history of New York Heart Association (NYHA) functional classification class III or IV heart failure due to factors other than hypertension.
  17. Patients with a history of myocardial infarction, unstable angina, percutaneous coronary intervention, coronary artery bypass grafting, or stroke or major surgery 24 weeks before screening.
  18. Patients with a history of substance abuse.
  19. Patients with malignant tumors.  
Patients who have undergone radical surgery, patients who have completed chemotherapy/radiation therapy and patients who are undergoing hormone therapy can be registered.
  20. Patients with known intolerance to MRI or patients who are contraindicated for MRI examination.
  21. Other patients who the principal or sub-investigator deems inappropriate for conducting this clinical trial.

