**【Setting basis】**

- (1)(3)(5)-(7) were set because they may affect the evaluation of efficacy in this study.
- (2) was set since it is the same active ingredient as the investigational drug, it affects the evaluation of efficacy in this study and ensures safety
- (4) was set because there is a risk of enhancing or diminishing the action when used in combination with an investigational drug.

2. From the time of screening to the follow-up end, the following therapies are prohibited:

- (1) Obesity surgery (sleeve gastrectomy, gastric bypass surgery, sleeve bypass surgery, etc.)

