### 8.3.2 Continued use of pretreatment and combination therapy

When the following drugs and therapies are used in combination during the treatment period, they can be used under the conditions described.

1. Drugs restricted for concomitant use include:

- (1) Antihypertensive drug
- (2) Drugs to treat dyslipidemia
- (3) Drugs to treat diabetes treatment (DPP-4 inhibitor, SU preparation,  $\alpha$ -glucosidase inhibitor, metformin)

The above concomitant drugs may be used concomitantly only if the dose is kept constant from 12 weeks before screening and the drug is continuously used. The dose is not changed until the end of the investment drug administration.

\* Regarding antihypertensive drugs, if symptoms worsen, additional administration of only calcium antagonists is possible.

\* Regarding diabetes treatment drugs, if the symptoms worsen, the dose can be gradually reduced.

The use of drugs for concomitant use after the end of the administration of the investigational drug is not restricted.

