### 8.5 Overall flow of this clinical trial

#### 8.5.1 Consent acquisition

The principal investigator or sub-investigator obtains written consent from the subject at the time of screening in accordance with “エラー! 参照元が見つかりません。 エラー! 参照元が見つかりません。” of this clinical trial protocol. After obtaining consent, the required items are completed in the "Subject Screening List".

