## 9 Observation, inspection, evaluation items, and timing

### 9.1 Observation, inspection, and evaluation schedule list

The principal investigator or sub-investigator conducts observations, inspections, surveys, etc. according to the table below. If a blood sampling test is to be performed at the time of the subject's visit, the subject should fast for 8 hours before the blood is collected.

Table 9.1-1 Observation, examination, and evaluation schedule

		8-week	16-week						4-week
Screening		Group A: WY-8678 4 mg/day: one tablet per session, twice per day						Follow-up	
		Group B: WY-8678 8 mg/day: 2 tablets per session, twice per day							
Week	Consent acquisition	Screening	Treatment period						Follow-up
		V1	V2	V3	V4	V5	V6	V7/EOT	V8
		Within 8 weeks prior to registration	Prior to start of administration	2 weeks	4 weeks	8 weeks	12 weeks	16 weeks	4 weeks after end of administration
Tolerable range		-8 weeks	-	±3 days	±7 days	±7 days	±7 days	±7 days	±7 days
Consent acquisition	○								
Selection criteria		○	○						
Subject background		○							
Serological test a		○							
Chest X-ray		○							
Electro-cardiogram		○							
Physical examination b		○	○					○	
Vital signs c		○	○	○	○	○	○	○	○
Subjective and objective symptoms			○	○	○	○	○	○	○
Pregnancy test d			○					○	
MRI e		○						○	
Liver biopsy		△							
Randomization			○						
Hematology test / urine test f		○	○ i					○	○
Endocrinological examination		○							
Biochemical test 1		○	○ i		○	○	○	○	○
Biochemical test 2 g		○	○ i					○	
Other h			○					○	
Somatic cell genetic test			●						
Providing drugs			○		○	○	○		
Checking the medication status				○	○	○	○	○	
Survey of combination drugs		○	○	○	○	○	○	○	
Investigation of adverse events				○	○	○	○	○	○

○: Implemented

△: Information is collected for cases with liver biopsy results (within 32 weeks before screening).

●: Genetic testing is an essential test.

a: Contains HBs antigen, HCV antibody, and HCV-RNA.

b: Includes height (V1 only) and weight. BMI (V1) is calculated based on height and weight.

c: Vital signs include blood pressure, pulse rate, and axillary body temperature.

d: For women of childbearing potential, a urine pregnancy test will be performed on V2 and V7.

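### Clonidine and methyldopa are barred from consent because they affect the efficacy evaluation, but section 4.3 has no matching prior-use exclusion, so a stable user could have the only baseline PDFF scan with little or no time off drug

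*Protocol*

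**What the plan says.** Section 8.3.1 prohibits "2) Guanabenz analogs (clonidine, methyldopa") from consent through the treatment period. The setting basis beneath it says that item "2) was set since it is the same active ingredient as the investigational drug, it affects the evaluation of efficacy in this study", and adds safety as a further reason.

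The prior-use rules in section 4.3 are narrower:

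- Exclusion 2 covers "Patients who have taken guanabenz acetate within 16 weeks prior to screening". The Summary carries the same criterion. Neither names the analogs.
- Exclusion 10(3) covers "Altered doses of dyslipidemia drugs or antihypertensive drugs 12 weeks before screening", which is a rule about change of dose and not about use.

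Section 8.3.2 states that background antihypertensives "may be used concomitantly only if the dose is kept constant from 12 weeks before screening and the drug is continuously used". It does not say how an antihypertensive that 8.3.1 bars is to be handled.

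On timing, section 8.5.1 says that the investigator "obtains written consent from the subject at the time of screening". Table 9.1-1 places V1 "Within 8 weeks prior to registration". MRI-PDFF is listed at V1 (8.5.2) and at V7/EOT (8.5.6) but not at V2 (8.5.3). No minimum time off a prohibited drug before the V1 scan is stated.

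**The concern.** The plan itself says that these two drugs affect the efficacy evaluation, yet it protects the treatment period from them and leaves the baseline open. For a patient who comes off clonidine or methyldopa at consent, the change in PDFF from V1 to week 16 combines stopping an analog with starting guanabenz. The primary analysis (13.4.1) compares one pooled responder proportion with a fixed 0.25. With no placebo arm, the design cannot separate the two.

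The omission looks like an oversight because every other drug class listed in 8.3.1 has a counterpart in 4.3. The one class without a counterpart is the class that the setting basis equates with the study drug.

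**Working it through.** **Step 1: match each class prohibited in 8.3.1 with its prior-use rule in 4.3.**

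| Prohibited in 8.3.1 | Prior-use rule in 4.3 |
|---|---|
| (1) Ursodeoxycholic acid | 10(2), 12 weeks |
| (2) Clonidine, methyldopa | none (exclusion 2 names guanabenz acetate only, 16 weeks) |
| (3) Thiazolidine, GLP-1 agonist, SGLT2 inhibitor, insulin | 10(1), 12 weeks |
| (4) CNS depressants | 10(6), no period stated |
| (5) Vitamin E | 10(2), 12 weeks |
| (6) NAFLD-related drugs and hepatotoxins | 9, 4 weeks |
| (7) Drugs affecting body weight | 10(5), 12 weeks |

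Only item (2) has no counterpart.

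**Step 2: follow a patient on a stable clonidine dose through the written criteria.**

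- Exclusion 2: not met, because the patient has not taken guanabenz acetate.
- Exclusion 10(3): not met, because the dose has not changed in the 12 weeks before screening. A user who stopped during those 12 weeks could be excluded. Among recent users, the rules therefore favour those with the least time off drug.
- Exclusion 10(6): the list of CNS depressants is open-ended but names neither drug, and 8.3.1 treats CNS depressants as a separate item (4).
- Exclusion 21: discretionary.
- V2: the schedule rechecks the same selection criteria and adds nothing.

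The patient is eligible as written and, under 8.3.1, may not use the drug from consent.

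**Step 3: timing of the baseline scan.** If consent and V1 fall on the same day, time off drug at the scan can be zero. V1 may precede registration by up to 8 weeks. The interval from the V1 scan to week 16 can therefore include 0 to 8 weeks with neither drug, followed by 16 weeks of guanabenz (visit windows ignored).

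**Step 4: reproduce the design.** Inputs from 13.1: n = 28, null 0.25, alternative 0.5, one-sided 5%. Exact binomial:

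- The smallest r with P(X ≥ r | 28, 0.25) ≤ 0.05 is 12.
- Size is P(X ≥ 12 | 28, 0.25) = 0.0294.
- Power is P(X ≥ 12 | 28, 0.5) = 0.8275.
- The lower limit of the 90% Clopper-Pearson interval is 0.269 at 12/28 and 0.238 at 11/28, so the interval rule gives the same cut-off.

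The planned 28 cases do give at least 80% power.

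**Step 5: illustration under assumed inputs.** The documents give neither a count of users nor a direction of effect. Assume m users with response probability pu, and 28 − m patients at p. For m = 1:

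P(success) = (1 − pu) × P(X ≥ 12 | 27, p) + pu × P(X ≥ 11 | 27, p)

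- Power with p = 0.5 and pu = 0.25: 0.75 × 0.7790 + 0.25 × 0.8761 = 0.8033.
- Power with p = 0.5 and pu = 0.75: 0.25 × 0.7790 + 0.75 × 0.8761 = 0.8518.
- Size with p = 0.25 and pu = 0.50: 0.5 × 0.0216 + 0.5 × 0.0528 = 0.0372.

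| Users m | Power, shift of ∓0.25 | Size, shift of +0.25 | Power, pu = 0 or 1 | Size, pu = 0 or 1 |
|---|---|---|---|---|
| 0 | 82.8% | 2.9% | 82.8% | 2.9% |
| 1 | 80.3% / 85.2% | 3.7% | 77.9% / 87.6% | 2.2% / 5.3% |
| 2 | 77.7% / 87.4% | 4.7% | 72.1% / 91.6% | 1.6% / 9.1% |

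The last two columns are outer bounds, with a user's responder status completely fixed. They are not expected effects.

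**The case against.** The strongest reply is that the protocol, read as a whole, leaves little room for this patient. The analog may not be continued (8.3.1), and 8.3.2 with its basis wants antihypertensive doses unchanged from 12 weeks before screening to the end of dosing. An investigator applying both would probably not enrol a current user. Both schedules also show consent in a column before V1. If the drug is stopped at consent and V1 is on a later day, 10(3) can be read to exclude the patient. No passage tells anyone to stop an established antihypertensive in order to enter. That step is inferred from the ban. The principal investigator at a single centre judges eligibility, and section 13.3 sends unusual cases to a case review committee.

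Part of this stands. The route is narrow, and it narrows further when consent and V1 are on different days. It does not close. Section 8.3.2 governs drugs continued during treatment and is not an eligibility criterion, 8.5.1 places consent at screening, and exclusion 21 and the committee are discretionary.

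A reader might infer that the gap biases the primary result or inflates its error rate. The documents do not support that. Section 1.2 attributes the liver effect to Helz2 binding, separate from the action on the nervous system, and nothing says that clonidine or methyldopa bind Helz2. Section 1.3 links the α2 action to reduced feeding and weight loss only as a possibility, at the high mouse dose. The setting basis calls the analogs the same active ingredient, but that wording is loose, since 8.3.1 itself calls them analogs.

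**Conclusion.** The gap holds as an inconsistency between 8.3.1 and 4.3. A stable user of clonidine or methyldopa meets every written criterion and could have the sole baseline PDFF scan with little or no time off drug. That rests on two readings: that the ban from consent means the drug is stopped then, and that consent and V1 can coincide.

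It is minor. The number of affected patients may be zero, in which case nothing changes, and the direction of any effect on PDFF is unknown. The power and size figures illustrate sensitivity under assumed inputs and are not consequences of the gap. With a shift of 0.25 in one or two users, size stays below 5% and power is 77.7% at worst. Size passes 5% only when a user's responder status is taken as completely fixed. The case for acting is that the plan's own premise calls for the protection and that providing it is cheap.

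**What to change.** In section 4.3 and in the Summary, extend exclusion 2 so that the 16-week look-back before screening covers guanabenz acetate or its analogs (clonidine, methyldopa). This applies to the analogs the period already set for the study drug.

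Optionally, add a sentence to 8.3.2 that the antihypertensive allowance does not extend to drugs listed in 8.3.1. This only clarifies what 8.3.1 already says.

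The cost is a few words in two places by amendment, and possibly a few fewer candidates, mainly current stable users. The sample size of 28 and the analysis do not change.
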